Region-level sensitivity, specificity, PPV, NPV, accuracy will be summarized respectively with corresponded exact 95% CI by regions. Region consists of liver, pancreas, gastrointestinal, lymph nodes and others.

Number of lesions detected by imaging

For region-level, number of lesion detected by [⁶⁸Ga]Ga-DOTA-TATE PET/CT imaging and CIM will be counted. Regarding [⁶⁸Ga]Ga-DOTA-TATE PET/CT imaging, individual and mean number of lesions detected by each 3 central readers will be presented. Regarding CIM, each number of lesions detected by [¹¹¹In]In-Pentetreotide SPECT/CT and High Resolution CT with contrast (or MRI if CT with contrast is medically contraindicated) will be presented.

Impact on treatment decision

Numbers and percentages of participants for each intended treatment plan collected from physician at pre and post [⁶⁸Ga]Ga-DOTA-TATE PET/CT imaging will be summarized. Summary statistics of participants for the change of intended treatment plan will also be presented.

Inter-reader variability

Inter-reader variability for [⁶⁸Ga]Ga-DOTA-TATE PET/CT imaging is defined as agreement rate among reader determinations and will be assessed by Fleiss' Kappa statistics. Inter-reader variability (%) and its normality 95% CI will be presented.

Lesion-level concordance rate for SSTR

The lesion-level concordance rate for SSTR between [⁶⁸Ga]Ga-DOTA-TATE PET/CT imaging local read and local histopathology result among lesions which is available, will be calculated. The rate is defined as the proportion of lesions which are positive or negative on both local read of [⁶⁸Ga]Ga-DOTA-TATE PET/CT imaging and local histopathology among lesions detected by local histopathology.

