
Objective(s)	Endpoint(s)

• To evaluate inter-reader variability.• To evaluate safety and tolerability of [68Ga]Ga-DOTA-TATE.• To evaluate PK of [68Ga]Ga-DOTA-TATE.• To evaluate lesion-level concordance for SSTR between [68Ga]Ga-DOTA-TATE PET/CT imaging local read and local histopathology results.	
• Inter-reader agreement on [68Ga]Ga-DOTA-TATE PET/CT imaging.• Incidence of Treatment emergent adverse event (TEAE) within 8 days after [68Ga]Ga-DOTA-TATE administration.• Pharmacokinetic parameters (AUCinf, AUClast, Cmax, Tmax, T1/2, CL, Vz etc.).• Lesion-level concordance rate for SSTR between [68Ga]Ga-DOTA-TATE PET/CT imaging local read and local histopathology result among lesions that local histopathology result are available.

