2.6.2 Statistical hypothesis, model, and method of analysis

Subject-level assessments

Subject-level PPV, NPV, accuracy will be summarized with corresponding exact 95% CI.

Region-level assessments

Region-level sensitivity, specificity, PPV, NPV, accuracy will be summarized respectively with corresponding exact 95% CI by regions.

Region consists of liver, pancreas, gastrointestinal, lymph nodes and others.

Number of lesions detected by imaging

Descriptive statistics for number of lesions will be provided by region-level and subject-level.

Regarding [⁶⁸Ga]Ga-DOTA-TATE PET/CT imaging, descriptive statistics of number of lesions for each of the 3 central reader , and 3 readers' mean number of lesions will be presented.

Regarding CIM, descriptive statistics of number of lesions detected by [¹¹¹In]In-Pentetreotide SPECT/CT and High Resolution CT with contrast (or MRI if CT with contrast is medically contraindicated) will be presented respectively.

Listing for number of lesions will be provided.

Impact on treatment decision

The number (%) of participants for intended treatment plan at pre and post [⁶⁸Ga]Ga-DOTA-TATE PET/CT imaging and the number (%) of participants for whom the intended treatment plan has changed and for whom it has not changed will be summarized. The number (%) of

participants will also be summarized for each combination of transition of intended treatment plan.

Listing for intended treatment plan will be provided.

Inter-reader variability

Each central read subject-level result (positive or negative), inter-reader variability (%) and its 95% CI will be presented.

Inter-reader variability will be assessed by Fleiss' Kappa (κ_1) statistic ([Fleiss 1971](#)). Refer to [Section 5.4.2](#) for details on Fleiss' Kappa.

An additional table will be presented to show the distribution of agreements with the number (%) of scans agreed by two readers and the number (%) of scans agreed by all three readers.

If one of the central readers is changed during the study and the total amount of its read is more than 30% of the total number of participants who have evaluable [⁶⁸Ga]Ga-DOTA-TATE PET/CT, inter-reader variability for each combination (before the change and after the change) and its normality 95% CI will be presented additionally. The distribution of agreements with the number (%) of scans agreed by two readers and the number (%) of scans agreed by all three readers will be also presented for each combination.

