5.4.2 Analysis supporting secondary objective(s)

For subject-level assessments and region-level assessments, their estimation and 95% CI will be calculated based on the binomial distribution (implemented using SAS procedure FREQ with EXACT statement for one-way tables) ([Clopper and Pearson 1934](#)).

For inter-reader variability, it will be assessed by Fleiss' Kappa (κ_1) statistic ([Fleiss 1971](#)) defined below:

$$\kappa_1 = \frac{\bar{P} - \bar{P}_e}{1 - \bar{P}_e}.$$

Let N represent the total number of participants who have evaluable $[^{68}\text{Ga}]$ Ga-DOTA-TATE PET/CT, n the number of central readings per participants received ($n = 3$), and k the number of outcome categories ($k = 2$). Participants are indexed by $i = 1, \dots, N$ and categories are indexed by $j = 1, \dots, k$. Let n_{ij} represent the number of readers who assigned the i th participant to the j th category. Then

$$P_i = \frac{1}{n(n-1)} \sum_{j=1}^k n_{ij} (n_{ij} - 1) \text{ and } \bar{P} = \frac{1}{N} \sum_{i=1}^N P_i ;$$
$$p_j = \frac{1}{Nn} \sum_{i=1}^N n_{ij} \text{ and } \bar{P}_e = \sum_{j=1}^k p_j^2.$$

A contingency table of N row by 2 (the number of outcome categories) will be obtained to summarize the frequency of agreements among the 3 readers for each case and each patient-level outcome (i.e. positive, negative). The counts across each of the N rows will sum up to 3 (number of readers).

Based on the contingency table as described above, a Fleiss's Kappa statistic and corresponding 95% confidence interval will be estimated based on asymptotic estimation of the standard error

$$(\text{i.e. } \widehat{se}(\kappa_1) = \frac{\sqrt{2}}{\sum_{j=1}^k p_j(1-p_j)\sqrt{Nn(n-1)}} \sqrt{\left(\sum_{j=1}^k p_j (1-p_j)\right)^2 - \sum_{j=1}^k p_j(1-p_j)(1-2p_j)})$$

([Fleiss, Nee, Landis 1979](#); [Fleiss J, Levin B, Paik MC 2003](#)) and the normality assumption (i.e. 95% CI can be calculated as: $\kappa_1 \pm 1.96\widehat{se}(\kappa_1)$).

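### The 95% CI for Fleiss' kappa uses the standard error that holds only at kappa = 0, so at N = 70 it is kappa ± 0.135 whatever agreement is observed

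*SAP*

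**What the plan says.** SAP Table 1-1 lists the objective "To evaluate inter-reader variability", with inter-reader agreement on the PET/CT as its endpoint. Protocol 9.4.1 promises that "Inter-reader variability (%) and its normality 95% CI will be presented".

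SAP 5.4.2 defines Fleiss' kappa for three readers and two categories (positive, negative). It then states that "a Fleiss's Kappa statistic and corresponding 95% confidence interval will be estimated based on asymptotic estimation of the standard error", prints the formula, "and the normality assumption (i.e. 95% CI can be calculated as" kappa ± 1.96 × SE. Neither document gives another variance or bounds the upper limit at 1.

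SAP 2.6.2 asks for the same kind of interval again if a central reader is replaced and read more than 30% of the evaluable participants: "inter-reader variability for each combination (before the change and after the change) and its normality 95% CI will be presented additionally". SAP 5.4.2 gives the only standard error available for that analysis. SAP 2.6.2 also tabulates "the number (%) of scans agreed by all three readers".

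**The concern.** The printed standard error depends on N, the number of readers and the marginal proportions of positive and negative reads. The observed agreement does not enter it. That form suits a test of no agreement beyond chance, but no such test is planned. Here it is used for an estimation interval, where the sampling variance of kappa changes with kappa itself.

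For a descriptive endpoint the estimate and its interval are the whole result. At moderate agreement, where reader reliability is most in doubt, the lower limit would be overstated. At high agreement the report could show upper limits above 1.

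**Working it through.** **Inputs.** From SAP 5.4.2: n = 3 readers, k = 2 categories, N = participants with an evaluable PET/CT, and the interval kappa ± 1.96 × SE. From SAP Section 3: 70 participants (47 patients, 23 healthy volunteers), with expected sensitivity and specificity of 90%. The documents state no kappa SE or width to reproduce. The power behind N = 70 does reproduce with the exact binomial test: n = 47, success at 40 or more, power 90.7%; n = 23, success at 19 or more, power 92.7%.

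**Algebra.** The printed formula is

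SE = √2 / [Σp_j(1−p_j) · √(N n (n−1))] × √{[Σp_j(1−p_j)]² − Σp_j(1−p_j)(1−2p_j)}.

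With two categories, p and q = 1 − p:

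- Σp_j(1−p_j) = 2pq
- Σp_j(1−p_j)(1−2p_j) = pq(1−2p) + pq(1−2q) = 2pq(1 − p − q) = 0

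The factor 2pq cancels for any 0 < p < 1, leaving SE = √(2/(N·3·2)) = 1/√(3N). At N = 70 this is 1/√210 = 0.0690, and the half-width is 1.96 × 0.0690 = 0.135. Putting p = 0.5, 0.64 and 0.9 into the full formula gives 0.0690 each time. The half-width is 0.140 at N = 65 and 0.131 at N = 75. The upper limit passes 1 when kappa exceeds 1 − 0.135 = 0.865.

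**Correct width.** The delta-method half-width at N = 70, with a positive-read share of 0.64 and a common-correlation model, is:

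| kappa | 0 | 0.2 | 0.4 | 0.6 | 0.7 | 0.8 | 0.9 |
|---|---|---|---|---|---|---|---|
| Correct | 0.135 | 0.161 | 0.166 | 0.152 | 0.138 | 0.118 | 0.086 |
| SAP | 0.135 | 0.135 | 0.135 | 0.135 | 0.135 | 0.135 | 0.135 |

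The two agree at kappa = 0, and nearly so around 0.7, where the match is a coincidence.

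**Coverage.** Simulation with 100,000 trials per row, exactly 47 patients and 23 healthy volunteers, equal per-reader accuracy and independent errors (all assumptions). The SAP SE is 0.069 in every row.

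| Reader accuracy | kappa | True SD | SAP coverage | Upper limit > 1 |
|---|---|---|---|---|
| 80% | 0.33 | 0.080 | 90.7% | 0% |
| 85% | 0.46 | 0.079 | 91.0% | 0% |
| 90% | 0.61 | 0.074 | 92.9% | <0.1% |
| 93% | 0.71 | 0.067 | 95.5% | 1% |
| 95% | 0.79 | 0.060 | 97.6% | 11% |
| 97% | 0.87 | 0.050 | 99.3% | 59% |

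If the patient/volunteer split is drawn at random at 67% instead of fixed, coverage is about one point lower at 80% and 90% accuracy (89.7% and 91.7%). Correlated errors at 90% accuracy (assumed intraclass correlation 0.3 and 0.5) raise kappa to 0.73 and 0.81 and coverage to 96.1% and 98.2%.

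**Two worked examples, N = 70** (scans with 3/2/1/0 positive reads). A unanimous scan has P_i = 1 and a split scan P_i = 1/3.

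- 35/12/6/17: mean agreement (52 + 18/3)/70 = 0.829; p = 135/210 = 0.643; chance agreement 0.541; kappa = (0.829 − 0.541)/(1 − 0.541) = 0.627. SAP interval 0.491 to 0.762. The jackknife SE is 0.0777, so the log(1 − kappa) factor is exp(1.96 × 0.0777/0.373) = 1.503. The limits are 1 − 0.373 × 1.503 = 0.439 and 1 − 0.373/1.503 = 0.752.
- 42/2/2/24: kappa 0.918. SAP interval 0.783 to 1.054. With jackknife SE 0.0400, the log(1 − kappa) interval is 0.787 to 0.969.

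**Reader change (contingent, illustrative).** If the 30% condition is just met, with N = 22 as 15 patients and 7 volunteers, the SAP half-width is 1.96/√66 = 0.241. Coverage is 90.3%, 91.7%, 97.7% and 99.0% at accuracy 80%, 90%, 95% and 97%.

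**The case against.** The strongest reply is that little depends on this interval. No threshold, test or alpha attaches to it. The agreement counts in SAP 2.6.2 do not use the standard error, and SAP 2.5.6 gives per-reader sensitivity and specificity with exact intervals if the co-primary endpoints are met. At 90% reader accuracy the coverage loss is about 2 points. At high kappa the interval is too wide, which does not flatter the product. Correlated reader errors are plausible when readers see the same images, and they remove the narrowness at that accuracy. Reading the planned 90% as a per-reader accuracy is itself an assumption. All of this stands. It limits the weight of the point and means that undercoverage cannot be predicted for this trial.

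It does not rescue the formula: an interval whose width cannot respond to the observed agreement does not measure the precision of that estimate. Capping at 1 would remove impossible values without changing coverage.

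It is also fair that any non-null variance would cure the core defect, and that the replacement proposed here covers slightly above 95% under the fixed split (96.0% at 90% accuracy). The replacement also has to be reconciled with the interval named in Protocol 9.4.1.

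**Conclusion.** The concern holds. The reduction to 1/√(3N) is exact and needs no assumption beyond the SAP's own two categories and three readers. The coverage figures rest on the assumed reader models and case mix.

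Under those models, coverage at N = 70 with the fixed split runs from 90.7% at 80% reader accuracy to 99.3% at 97%. The crossover is near kappa 0.7 for positive-read shares of about 0.5 to 0.67. At a much more extreme share the interval stays too narrow further up (share 0.9, kappa 0.8: about 79% to 81%), but the planned 47:23 mix makes that unlikely.

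The damage is confined to the precision statement of one descriptive secondary endpoint. It should be fixed, but it does not threaten the trial's main conclusions.

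**What to change.** In SAP 5.4.2, and for the reader-change analysis in SAP 2.6.2, replace the standard error with a participant-level jackknife SE applied on the log(1 − kappa) scale:

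1 − (1 − kappa) × exp(±1.96 × SE/(1 − kappa)).

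This cannot pass 1. Its simulated coverage under the fixed split is 95.3% to 96.5% at N = 70 and 94.2% to 96.8% at N = 22, leaving out trials with perfect agreement. The delta-method SE on the same scale is an acceptable substitute at N = 70 (94.9% to 96.2%). A percentile bootstrap over participants is acceptable at N = 70 (93.7% to 95.6%), but not for the reader-change subset: at N = 22 and 97% accuracy it covers 85.5% if perfect-agreement trials count as misses.

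Add a rule for perfect agreement, where these intervals are undefined or have zero width. Report kappa = 1 without a kappa interval, and give the Clopper-Pearson interval for the proportion of scans on which all three readers agree. The lower limits are 0.025^(1/70) = 94.9% for 70/70 and 0.025^(1/22) = 84.6% for 22/22. Keep the present SE only if a test of kappa = 0 is ever wanted.

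The cost is SAP wording, a one-line entry in SAP Section 4 to reconcile the change with Protocol 9.4.1, and a few lines of code; SAP 2.1 already lists R. No new data are needed. At N = 70 the mean interval width rises from 0.271 to 0.311 at 90% accuracy and falls to 0.218 at 97%. In an N = 22 subset it is wider throughout (0.53 to 0.63 against 0.48).

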5.5 Classification of NEN

Entries as Other in the eCRF Diagnosis of Disease are classified as NET, NEC, or Other NEN based on specified terms according to the [Table 5-3](#). NENs not specified in [Table 5-3](#) will be classified as Other NENs, and a separate .xlsx file will be created to specify the details as needed. Diseases other than NEN will be classified as Other.

Table 5-3 Classification of NEN

Terminology	Classification of NEN
Carcinoid	NET
Merkel cell carcinoma	NEC
Mixed Neuroendocrine-non-neuroendocrine Neoplasm (MiNEN)	MiNEN
Paraganglioma	Other NEN

5.6 Primary Site of Cancer corresponding to GEP-NET

GEP-NET to which NET grading will be applied is defined as patients with following Primary Site of Cancer in the eCRF Diagnosis of Disease.

- Anal canal
- Appendix
- Cecum
- Colon
- Colon, ascending
- Colon, descending
- Colon, sigmoid
- Duodenum
- Esophagus
- Fundus of the stomach
- Gastroesophageal junction
- Greater curvature of the stomach
- Ileum
- Ileum, terminal
- Jejunum
- Left colon
- Lower third of the esophagus
- Middle third of the esophagus
- Pancreas
- Pancreatic duct
- Rectum

- Right colon
- Small intestine
- Stomach
- Stomach lesser curvature
- Transverse colon
- Upper third of the esophagus

5.7 Derivation of Mass-Based Dose and Concentrations

Blood concentration and dose values will be determined by radioactivity measurements performed at the clinical sites. Radioactivity-based concentration values will be converted to mass-based concentration values using the specific activity of the dosing solution (MBq of radioactivity/ μ g of ligand), taking into account the times at which the specific activities are measured, doses are administered, samples are collected and samples are measured. Radioactivity-based dose values will be converted to mass-based dose values using the fixed amount of mass dose of DOTA-TATE cold kit (40 μ g) and radioactivity values after radiolabeling, taking into account the times at which radioactivity values are measured and doses are administered. All necessary information needed to perform these conversions will be captured in the dose preparation, study treatment, gamma counter calibration and blood collection eCRFs. The detailed instructions for how to perform these conversions will be described in a separate document (supplement to SAP).

6 Reference

Clopper CJ, Pearson ES (1934) The use of confidence or fiducial limits illustrated in the case of the binomial. *Biometrical*, 26, 404-413.

Fleiss J. L. (1971). Measuring nominal scale agreement among many raters. *Psychological bulletin*; 76(5): 378-382.

ICH E9(R1) Harmonized Guideline: addendum on estimands and sensitivity analysis in clinical trials to the guideline on statistical principles for clinical trials. Final version on 20 November 2019.
